7.2.2. Sampling for scientific purposes

For the investigation of molecular mechanisms of sorafenib resistance development, biomarkers of response, sorafenib plasma levels, and gene regulations associated with study medication, peripheral blood samples (20 ml heparinized blood and 10 ml serum) shall be sent at baseline and every 6 months thereafter (table 6) to [name]. [name], Molecular laboratory in Marburg. 20ml of heparin bone marrow will be shipped to the same laboratory only in case a biopsy is performed, that is, at baseline and in relapse. Shipment is recommended from Monday through Thursday via 12h express delivery to
Universitätsklinikum Gießen und Marburg GmbH
[name]. [name]
Molekularbiologisches Labor
[name]
[name]

A sample accompanying form can be found in the ISF.

8. Duration of the study and the follow up period

Assuming an accrual time of 24 months and duration of treatment (of the last included patient) of 24 months the duration of the study will be approximately 48 months. The duration of the follow up period will be 6 months.

- Accrual time: 24 months
- First patient in to last patient out: 48 months
- Follow-up: 6 months
- Study period: 54 months excluding preparation and analysis
- Post study follow up: 12 months

9. Safety

In order to comply with the standards for Good Clinical Practice (GCP) it is important that investigators are aware of the different definitions related to adverse events and how to record, report and review each of these specific occurrences.

9.1. Definition of Adverse Event (AE)

An Adverse Event (AE) is any untoward medical occurrence in the patient administered a pharmaceutical product that does not necessarily have a causal relationship with this treatment. An AE is therefore described as any unfavourable and unintended sign (including laboratory result), symptom, or disease temporally (timely) associated with the use of a medicinal (investigational) product, whether or not related to the product.

The reporting of abnormal laboratory values should be avoided unless they lead to clinical consequences that are not routine.

Events such as nausea, vomiting or constipation should not be regarded as AE (unless Grade III / IV and worsening of symptoms after treatment start) until day +100 after transplantation.

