	
substance abuse, uncontrolled infection, known HIV, HBV, HCV infection
 
 • Psychiatric disorder that interferes with ability to understand the study and give informed consent, and/or impacts study participation or follow-up. • Cardiac disease: heart failure NYHA III/IV, unstable coronary artery disease (MI more than 6 months prior to study entry is permitted), serious cardiac ventricular arrhythmias requiring anti-arrhythmic therapy (beta-blockers or digoxin are permitted) • Resting blood pressure consistently higher than systolic 150 mmHg and/or diastolic 90 mmHg despite antihypertensive therapy • Patients undergoing renal dialysis • Evidence or history of severe non-leukemia associated bleeding diathesis or coagulopathy • Patients with uncontrolled seizure disorder despite medication • History of organ allograft (except for allogenic SCTX) • Patients with major surgery, open biopsy, or significant traumatic injury within 4 weeks prior to start of first dose of study drug • Serious non-healing wound, ulcer or bone fracture • Known Flt3-kinase inhibitor resistance • Previous Sorafenib therapy • Active (uncontrolled) graft versus host disease GvHD (> grade I) at time of randomization despite the use of adequate therapeutic measures • Investigational drug therapy outside of this trial during or within 4 weeks of study entry • Pregnancy or breast feeding • Allergy to study medication or compositions of excipients in study medication • Secondary allo-SCT • Previous or concurrent cancer curatively treated ≤ 3 years prior to study entry

Investigational therapy: dose/mode of administration/ dosing schedule
	
Product: Sorafenib, 200mg / tablet
 
Mode of administration: Oral, tablet
 
Dosing schedule: Dose level 1 (starting dose) : 2 tablets / day (1-0-1) Dose level 2 (escalated dose): 3 tablets / day (1-0-2) Dose level 3 (targeted dose) : 4 tablets / day (2-0-2)
 
 • Dose level 1 will be given for 2 weeks • Dose level 2 applies for 4 weeks • If dose level 2 is well tolerated, the targeted dose will be administered, starting 6 weeks after treatment initiation • Study medication will be administered up to 2 years or until relapse

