4.1. Objectives

4.1.1. *Primary objective*

Relapse free survival (RFS) of Flt3-ITD+ AML patients in complete hematological remission after allo-SCT receiving Sorafenib maintenance therapy versus placebo

4.1.2. *Secondary objectives*

- To compare the median overall survival (OS) of Flt3-ITD+AML patients in CHR after allo-SCT receiving Sorafenib maintenance treatment versus placebo
- To compare the median RFS and OS of Flt3-ITD+ AML patients with and without NPM mutations receiving Sorafenib versus placebo
- To compare the median RFS and OS of Flt3-ITD+AML patients in CHR after allo-SCT receiving Sorafenib maintenance treatment versus placebo depending on the baseline expression level of Flt3-ITD at diagnosis
- To compare the toxicity of Sorafenib maintenance versus placebo
- To longitudinally evaluate biomarkers associated with Sorafenib treatment response and Sorafenib resistance and correlation with RFS and OS
- To assess safety with type, severity graded by NCI CTC criteria version 4.02.

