5.2. Inclusion criteria

- Written informed consent
- Age ≥ 18 y.
- ECOG performance ≤ 1
- FLT3-ITD-positive AML
- Complete hematological remission (CHR) after allo-SCT
- CHR must be confirmed by bone marrow analysis within 14 days before randomization (CHR criteria are: $\leq 5\%$ marrow blasts, no peripheral blasts, blood platelet count $> 100/\text{nl}$, WBC count $> 3 \text{ G/L}$, ANC $> 1 \text{ G/l}$).
- Allo-SCT with a HLA-identical allo-family donor (FAM) or a matched unrelated donor (MUD) with up to 1 antigen mismatch acceptable (9/10)
- Time point of study treatment start of patients in CHR: between d+60 up to d+100 after allo-SCT
- Adequate organ function:

-
- Serum creatinine ≤ 1.5 x upper normal value
 - ALT, AST, AP ≤ 2.5 x upper normal value
 - Total bilirubin ≤ 1.5 x upper limit of normal
 - PT-INR/PTT ≤ 1.5 x upper limit of normal
 - Patients who are being therapeutically anticoagulated with an agent such as Coumadin or Heparin will be allowed to participate provided that no prior evidence of underlying abnormality in these parameters exists)
 - Negative serum pregnancy test within seven days prior to first dose in women of child-bearing potential (WOCBP)
 - WOCBP must use a double barrier method of contraception during the study and for 3 months following the last dose of study drug. WOCBP are defined as sexually mature women who have not undergone a hysterectomy or surgical sterilization or who have not been naturally postmenopausal for at least 12 consecutive months (i.e., who has had menses any time in the preceding 12 consecutive months).
 - Male subjects whose sexual partners are WOCBP must use a double barrier method of contraception, one of which includes a condom, during the study and for 3 months after the end of treatment.

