6.2. Sorafenib/placebo - dose modifications and delays

Sorafenib/placebo therapy will be taken according to defined dose levels:

Dose level 1 (starting dose) : 2 tablets / day (1-0-1)
 Dose level 2 (escalated dose): 3 tablets / day (1-0-2)
 Dose level 3 (targeted dose) : 4 tablets / day (2-0-2)

The starting dose will be dose level 1 in order to allow adaption to the drug and avoid acute toxicities. If after the run-in phase of 2 weeks dose level 1 was well tolerated (no probably related AE's > grade 1), the next dose level (dose level 2) will be commenced and maintained for the next 4 weeks. If, after this time, dose level 2 was well tolerated the targeted standard dose level (dose level 3) will be administered indefinitely. Dose level 3 is the targeted dose.

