6.2.1. Dose delay and modifications for non-hematological toxicity

In case of severe toxicities, dose reductions or delays will be required as specified in Table 2. It illustrates dose modifications for all non-hematologic toxicities according to CTCAE Version 4.02 in the CRF, except for skin toxicities, which will be detailed separately below. These recommendations pertain, if the adverse event is considered related to sorafenib.

Table 2: Non-hematologic criteria for dose delay and dose modification of sorafenib (except skin toxicity)^a

Grade	Dose Delay	Dose modification
0-2	none	No change
3	Interrupt until \leq grade 2 ^b	Resume with one dose level below last dose level ^c
4	OFF protocol therapy	OFF protocol therapy

a. Excludes nausea/vomiting that has not been pre-medicated, and diarrhea.

b. If no recovery within an up to 28-day delay, treatment will be permanently terminated unless the patient is deriving clinical benefit

c. The dose of study drug may be increased from the reduced dose level stepwise every 4 weeks to dose level 3 if tolerated (no re-appearance of non-hematological toxicity \geq grade 0-2). In case toxicity recurs, and repeated dose reductions are required (more than 2), treatment will be indefinitely performed with dose level 1. When this is also not tolerated study treatment will be permanently discontinued.

For the purpose of dose modifications, patients experiencing Hand-Foot syndrome should have their signs and symptoms graded according to the following system (see below). Other skin toxicities will be graded according to CTCAE Version 4.02.

- Grading for Hand-Foot Syndrome

Grade 1

Numbness, dysesthesia/paresthesia, tingling, painless swelling or erythema of the hands and/or feet and/or discomfort, which does not disrupt normal activities.

Grade 2

Painful erythema and swelling of the hands and/or feet and/or discomfort affecting the patient's activities.

Grade 3

Moist desquamation, ulceration, blistering or severe pain of the hands and/or feet and/or severe discomfort, which cause the patient to be unable to work or perform activities of daily living.

According to the grade and incidence of skin toxicity (including rash and hand-foot syndrome) for a given patient, the following dose modification schedule will be followed (see Table 3).

Table 3: Skin Toxicity Criteria for Dose Modification of Sorafenib

Toxicity Grade	Dose modification	Dose level after interruption

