Grade 1	Maintain dose level	Institute supportive measures
Grade 2 1 st appearance	Interrupt until resolved to grade 0-1	Resume with one dose level below the dose level prior to interruption ^a
2 nd or 3 rd appearance	Interrupt until resolved to grade 0-1	Resume with dose level 1 and maintain indefinitely
4th appearance	Decision whether to discontinue treatment permanently	
Grade 3 1 st appearance	Interrupt until resolved to grade 0-1	Resume with one dose level below the dose level prior to interruption ^a
2 nd appearance	Interrupt until resolved to grade 0-1	Resume with dose level 1 and maintain indefinitely
3 rd appearance	Decision whether to discontinue treatment permanently	

^a For patients who require a dose reduction for grade 2 or 3 rash or hand-foot syndrome, the dose of study drug may be increased subsequently to the targeted dose level after 4 weeks of therapy at the reduced dose without the appearance of rash or hand foot syndrome \geq grade 1.

Patients with discomfort due to hand foot syndrome may be treated with topical emollients, low potency topical steroids, or urea-containing cream; emollients and urea cream can be used early as a prophylactic measures to prevent extensive skin toxicity (see also

prophylactic measures [26] [27] [28]. All other grade 3 toxicities related to study drug result in a permanent dose reduction.

- Sorafenib-associated diarrhea

Diarrhea is a common side effect of sorafenib but is usually of low-to-moderate grade. It either resolves while treatment is continued, with appropriate anti-diarrhoic treatments, or once sorafenib is discontinued.

Appropriate prophylactic and/or therapeutic drugs that have been reported to be effective in the treatment of sorafenib-associated diarrhea are loperamide (4 mg after first loose stool, 2 mg after every other loose stool) or racecadotril (Tiorfan®) (one 100mg capsule three times daily). *However, an important differential diagnosis of Sorafenib associated diarrhoea in the context of allo-SCT is intestinal GvHD, which should be histologically confirmed or excluded via endoscopy of the sigmoid / colon.*

- Sorafenib-associated hypertension

The dose modification schedule for treatment emergent **hypertension** during sorafenib dosing should be followed (see table 4). Patients' blood pressure (BP) measurements will be monitored and appropriate treatment to effectively control hypertension under sorafenib-treatment is strongly recommended.

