6.7. Study medication start and discontinuation

6.7.1. Start

Patients in CHR after allo-SCT will receive sorafenib or placebo as a maintenance therapy according to the dosing schedule specified above (s. 6.2).

Treatment will start in CHR as early as possible after allo-SCT, that is, when full hematological recovery has occurred (no peripheral blasts, bone marrow blasts $\leq 5\%$, white blood cell count $> 3G/l$, platelets $>100G/l$), but earliest on day+60 and latest until day+100 after allo-SCT. Treatment will continue for two years or until relapse.

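### Section 9.1 ends its exemption for low-grade nausea, vomiting and constipation at day +100 from transplant instead of at the first dose, so up to 40 days on study drug go unrecorded for these events

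*Protocol*

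**What the plan says.** Section 9.1 first defines an AE broadly, as any unfavourable sign or symptom whether or not it is related to the product. It then adds: "Events such as nausea, vomiting or constipation should not be regarded as AE". That exemption runs to day +100 from transplant. A bracketed carve-out brings back events that are grade III/IV and that worsen after treatment start.

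The inclusion criteria (5.2) place the first dose "between d+60 up to d+100 after allo-SCT", and 6.7.1 presses for the early end of that window: "Treatment will start in CHR as early as possible after allo-SCT".

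Dosing builds up in steps (Synopsis; 6.2): level 1 for 2 weeks, level 2 for 4 weeks, then the target level, "starting 6 weeks after treatment initiation". Moving up from level 1 requires that it was well tolerated, explained in brackets as "no probably related AE's > grade 1".

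One secondary objective (4.1.2) is "To compare the toxicity of Sorafenib maintenance versus placebo". Sections 11.3 and 11.4 serve it by comparing AE numbers between arms with Fisher's exact test. The first such analysis comes once 20 patients have had at least 3 months of treatment.

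**The concern.** The exemption is anchored to the transplant date, but exposure begins at the first dose. Wherever the first dose comes before day +100, the two overlap. Nothing elsewhere in the protocol limits the exemption to the time before dosing or to symptoms already present at baseline.

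Within the overlap, a grade 1-2 event of this type that is new on drug is, by definition, not an AE. If sorafenib causes an excess of brief, low-grade gastrointestinal symptoms in the first weeks, that excess is what the rule removes, and the comparison leans towards no difference. How much is removed depends on each patient's start day.

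The overlap also covers the level-1 run-in, whose purpose is to check tolerability before the dose rises. Section 3.4 acknowledges limited experience with sorafenib toxicity alongside routine post-transplant medication, so early tolerability is something this trial can usefully measure.

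**Working it through.** **Inputs.** Start day S, from 60 to 100 (5.2, 6.7.1). End of exemption, day 100 (9.1). Level 1, 14 days; level 2, 28 days (Synopsis, 6.2). Treatment, 24 months, taken as 730 days. Minimum exposure at the first safety analysis, 3 months, taken as 91 days (11.3).

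**The plan's own figure.** Build-up = 14 + 28 = 42 days, which agrees with the stated six weeks.

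**Overlap.**
- Exempt days on drug: w = 100 − S
- At level 1: min(14, w)
- At level 2: min(28, max(0, w − 14))
- At the target level: max(0, w − 42), which is 0 for every S because w never exceeds 40

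| Start day | Exempt days on drug | Level 1 | Level 2 | Target level begins |
|---|---|---|---|---|
| +60 | 40 | 14 | 26 | +102 |
| +70 | 30 | 14 | 16 | +112 |
| +80 | 20 | 14 | 6 | +122 |
| +86 | 14 | 14 | 0 | +128 |
| +90 | 10 | 10 | 0 | +132 |
| +100 | 0 | 0 | 0 | +142 |

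Counting both end days adds one day to each total (1 to 41) and still leaves the target level untouched.

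**Escalation steps.** The step from level 1 to level 2 falls on day S + 14, which is no later than day +100 when S ≤ 86. For those starts the whole run-in is exempt. The step to the target level falls on day S + 42, at the earliest day +102, so an event still present then is an AE and counts.

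**Shares at the extreme (S = 60).** 40/42 = 95% of build-up; 40/730 = 5.5% of the treatment period. For a patient with exactly the 3-month minimum exposure at the first safety analysis, 40/91 = 44%. The same share is 20/91 = 22% for a day +80 start and 0 for a day +100 start, and it falls with longer exposure.

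**What is actually lost.** The exemption lapses at day +100, so a symptom that persists or comes back is recorded from then on. If Fisher's test compares patients with and without an event (an assumption; the protocol speaks only of numbers of AEs), the loss is confined to patients whose low-grade symptoms resolve by day +100 and do not recur. The protocol gives no event rates, onset times or start-day distribution, so neither that number nor any effect on power can be computed.

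**After the fix.** With the exemption ending at the first dose, w = 0 for every S.

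**The case against.** Three arguments on the other side carry weight.

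First, the carve-out can be read as two separate exceptions: grade III/IV events, and symptoms that worsen after treatment start. On that reading a low-grade symptom that is new or worse on drug is an AE, and only unchanged transplant symptoms are exempt. The joint reading is the more literal one, but it has the odd result of also exempting a grade III/IV event that is not a worsening, so the authors' intent is uncertain. This stands as an ambiguity; it does not remove the need to settle the wording.

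Second, the carve-out itself mentions treatment start, so the overlap was probably known, and keeping background symptoms out of the AE log after transplant is a legitimate aim. That aim justifies exempting pre-dose or unchanged symptoms. It does not justify exempting new or worsening ones on blinded drug, for which the placebo arm is already the control.

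Third, the practical effect is small. Table 2 makes no dose change for grade 0-2 events, SAE criteria (9.2) still apply, and the safety committee's stated review is of SAEs and SUSARs (13.1).

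A reader might also infer more than the text supports:
- **That 6.2 would push patients with drug-related grade 2 vomiting up to level 2.** It does not compel this. The test is whether the level was well tolerated, the AE clause is a bracketed gloss, and 5.8 lets the physician stop treatment.
- **That diarrhoea is exempt.** The list is open-ended but does not name it, and 6.2.1 handles it separately: "Diarrhea is a common side effect of sorafenib but is usually of low-to-moderate grade". Table 2's note also sets it apart: "Excludes nausea/vomiting that has not been pre-medicated, and diarrhea".
- **That the empty Baseline Screen cell in the AE row of Table 6 is a gap of its own.** Section 10.1 already requires AE reporting from consent, and 7.1.2 schedules history and physical examination. This and the diarrhoea question are points for clarification only.

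**Conclusion.** The point holds as a minor, cheaply corrected weakness. Read literally, 9.1 denies AE status to grade 1-2 nausea, vomiting, constipation and similar events for 0 to 40 days on drug, all before the target dose. Those that resolve by day +100 and do not recur drop out of the by-arm toxicity comparison and, literally, out of the bracketed criterion for leaving level 1.

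This rests on taking the carve-out as one joint condition; on the looser reading the loss largely disappears and only unclear wording remains. The 95% and 44% shares need a start on exactly day +60, and the 44% also needs exactly the minimum exposure, so they are upper limits and not typical values.

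It would be wrong to conclude that all early low-grade toxicity is missing, or that one arm is favoured by assignment. Events that persist or recur are recorded, and the rule applies to both blinded arms alike. The primary endpoint, SAE reporting and time at the target dose are unaffected.

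**What to change.** In 9.1, replace the day +100 end point of the exemption with the first dose of study drug. New or worsening symptoms of any grade from that dose onward are then AEs in both arms and count for the escalation criterion in 6.2. The carve-out's reference to worsening after treatment start no longer has a role and can be deleted, which settles the ambiguity. Symptoms present before dosing can be noted at the baseline history and examination already scheduled in 7.1.2. As a clarification, 9.1 could also say that diarrhoea is not among the exempt events.

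The cost is more low-grade AE entries, partly post-transplant background, for at most 40 days per patient. The placebo arm allows that background to be separated from a drug effect.

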9.2. Definition of Serious Adverse Event (SAE)

A Serious Adverse Event (SAE) is any untoward medical occurrence (whether considered to be related to study drug or not) that occurs at any dose and:

- Results in death or
- Is life-threatening or
- Requires in-patient hospitalization or prolongation of existing hospitalization or
- Results in persistent or significant disability/incapacity or
- Results in congenital abnormality/birth defect.

SAEs will be documented in the patient's chart and in the CRF. The forwarding of the SAE form will be documented in the ISF. A copy of the SAE will be filed with the investigator site file.

9.2.1. Other events to be treated as SAEs or treated like SAEs

This would be exposure to drug during pregnancy/lactation.

In principle, pregnancy and the lactation period are exclusion criteria. In the event of a pregnancy occurring during the course of a study, the subject must be withdrawn from study drug immediately. The Investigator-Sponsor must be notified without delay and the subject followed during the entire course of the pregnancy and postpartum period. This has to be documented by using the pregnancy forms- The signed and dated forms has to be stored in the investigator's site file by the responsible investigators. Parental and neonatal outcomes must be recorded even if they are completely normal and without AEs. But if a pregnancy fulfill the (serious) adverse criteria, the regular AE or SAE procedure has to be applied.

9.2.2. Exceptions from SAE-reporting

- a) Hospitalization for diagnostic or regularly therapy as provided in the clinical trial plan
- b) Hospitalization that was planned before inclusion of the patient in the study for elective operations or treatment.
- c) Hospitalization due to GvHD or coherent treatment
- d) Hospitalization for pre-emptive therapy of CMV.

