3.4. Risk-benefit assessment

Due to a lack of curative treatment alternatives, the prognosis of relapsed Flt3-ITD positive AML after allo-SCT is usually detrimental. Recent data demonstrated a remarkably high therapeutic efficacy of Sorafenib in refractory and relapsed Flt3-ITD positive AML, suggesting that a pre-emptive therapeutic approach after allo-SCT - as planned in this study – may offer to patients the chance to prevent relapse and thus lead to an increased overall survival. There has been limited experience as to the interference of Sorafenib with GvL / GvHD effects and the toxicity resulting from Sorafenib use in the context of a variety of prophylactic medications routinely taken by transplanted patients after allo-SCT. Casuistic treatment experiences suggest that these adverse events can be managed. However, the overall benefit-risk ratio for patients entering this study seems to be clearly favourable.

4. Outcome measures

Aim of this study is to utilize the Flt3-ITD leukemia specific activity of sorafenib after allo-SCT to prevent relapses in the high risk group of patients with Flt3-ITD positive AML.

Toxicity will be evaluated according to toxicity scale Common Terminology Criteria for Adverse Events v4.02 (CTCAE) at <http://evs.nci.nih.gov/ftp1/CTCAE>

GvHD will be documented using the cGVHD Symptom Tracking Chart on www.asbmt.org (see also Tables 5 and 6 in the appendix)

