- **Donor lymphocyte infusions (DLI) are not part of this trial, and are generally not planned**, because there is no experience regarding the potential of Sorafenib to aggravate a graft versus host response in the context of DLI. Sorafenib may alter the activation and function of immunologically relevant cellular sub-fractions and thus the efficacy, tolerability and side effects (elicitation of GvHD) of DLI. DLI may, however, be performed at the discretion of the treating physician.

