9.3. Definition of Adverse Drug Reaction (ADR)

This is defined as any noxious and unintended (harmful or unwanted) response to a medicinal product normally used in man for prophylaxis, diagnosis or therapy of diseases, or for modifications of physiological function, and is suspected to be related to the drug. A suspected ADR is fulfilled, if the causality is judged as possible or probable by the investigator.

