9.5. Definition of Suspected Unexpected Serious Adverse Drug Reaction

The definition of a SUSAR is a serious adverse drug reaction or Serious Adverse Events related to Sorafenib, the nature or severity of which is not consistent with the applicable product information and therefore is considered “unexpected” with regard to the valid Summary of Product Characteristics for Sorafenib.

A serious event or drug reaction is not defined as a SUSAR when:

- a) It is serious, but expected;
- b) It does not fit the definition of a SAE or SADR, whether expected or not.

10. Recording, reporting and reviewing

It is the investigators responsibility to maintain an accurate and up to date record of all adverse events/occurrences in patients participating in the clinical trial. This record, including details of nature, onset duration, severity, outcome and any relationship to investigational product, should be made on the relevant documentation as specified below. Medical terminology according to CTCAE Version 4.02 should always be used to describe any event. Investigators should avoid vague terms such as “sick”. For details on assessing causality, see section 10.4 below.

It is the investigators responsibility to review all events occurring at their site and as such, the investigator must ensure that the patients are not compromised. Any appropriate action must be taken to protect the patients whilst ensuring validity of the results.

10.1. *Reporting of Adverse Events*

Adverse events will be reported on CRFs from the time the informed consent is signed, up to and including 30 days following last administration of study drug. In case that a patient has an open AE at the end of the study, it has to be reported until the AE is resolved or got the status unresolvable or the data base is closed. If the patient needs a therapy different from the clinical trial for treatment of the same indication, the reporting of the AE ends at the beginning of this therapy.

The severity of AEs will be graded according to the National Cancer Institute Common Terminology Criteria for AEs (CTCAE) 4.02 for Cancer Clinical Trials.

10.2. *Reporting of Serious Adverse Events*

All SAEs have to be recorded from the time the informed consent is signed, up to and including 30 days following last administration of study drug on the appropriate SAE pages in the CRF. Ongoing SAEs have to be reported every four weeks.

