The Investigator must fax or E-mail all serious adverse events (SAEs) to the KKS within 1 working day after awareness of the event. Where possible, a diagnosis rather than a list of symptoms should be given. The Investigator should complete all the details requested including dates of onset, severity, corrective therapies given, outcome and opinion as to whether the adverse event is likely to be drug-related. The Investigator should not wait for full details before making the initial report. Personal data have to be replaced by the trial patient number before forwarding any information.

If the event is fatal or life threatening, the Investigator must fax any relevant follow-up information of the reported SAE to the KKS within additional 8 days. If the reported SAE is not fatal or life threatening, the investigator must fax follow-up information as soon as possible.

In case of death, the Investigator has to supply Principal investigator, KKS, Competent Authority and Ethics Committee with all details requested.

The Principal Investigator will review the SAE again for seriousness and relatedness and assess the SAE for expectedness according to Summary of Product Characteristics (Product Information) or Investigator's Brochure as applicable.

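### Section 9.2.2(c) leaves GvHD that is serious by hospitalisation alone without a triggered SUSAR assessment, even when it is suspected to be drug-related or follows DLI on study drug

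*Protocol*

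**What the plan says.** Section 9.2 of the protocol defines an SAE regardless of relationship to study drug. One of its criteria is "Requires in-patient hospitalization or prolongation of existing hospitalization". Section 9.2.2 then lists exceptions from SAE reporting, of which item (c) is "Hospitalization due to GvHD or coherent treatment". The item is not limited by causality, grade or a preceding DLI.

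Elsewhere the protocol treats GvHD as an open safety question for this drug. Section 3.4 states "There has been limited experience as to the interference of Sorafenib with GvL / GvHD effects". Section 6.1.2.3 says that "there is no experience regarding the potential of Sorafenib to aggravate a graft versus host response in the context of DLI", describes DLI as generally not planned, and then adds "DLI may, however, be performed at the discretion of the treating physician". It attaches no reporting rule to a DLI and does not require study drug to be stopped.

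On causality, section 9.3 states "A suspected ADR is fulfilled, if the causality is judged as possible or probable by the investigator". On expedited reporting, section 10.2 states "The Investigator must fax or E-mail all serious adverse events (SAEs) to the KKS within 1 working day after awareness of the event".

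**The concern.** Exempting routine post-transplant GvHD admissions from SAE forms is reasonable, because GvHD is common enough after allo-SCT to swamp the reporting system. The difficulty is that the exception also takes in the admissions for which individual reporting is meant: those where the investigator suspects the study drug, and those where a DLI was given while the patient was taking it.

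For the suspected cases, the sections do not fit together. The definitions still class such an admission as a serious adverse drug reaction, and section 10.3 obliges the KKS to report it if it is also unexpected. Yet 9.2.2(c) removes the only stated step that puts the case in front of the people who would make that judgement. At stake is timely case-level recognition of a drug effect on GvHD, a risk that the protocol itself names as poorly known. The efficacy analysis is not affected.

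**Working it through.** No arithmetic applies. The check follows one case through the sections.

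Take a patient on study drug who is admitted with GvHD that is neither fatal, life-threatening nor disabling, and which the investigator grades as possibly related.

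1. **Seriousness (9.2).** Admission alone meets the criterion, so the event is serious by definition.
2. **Exception (9.2.2).** Item (c) applies and no SAE report is required. The section is headed as exceptions from reporting; it does not change what counts as serious.
3. **Drug reaction (9.3, 9.4).** Grading the event as possible makes it a suspected ADR. Being serious, it is a serious ADR.
4. **SUSAR (9.5).** If it is unexpected against the product information, it meets the SUSAR definition. The carve-out in 9.5(b), for events that do not fit the SAE or serious ADR definition, does not exclude it, because steps 1 and 3 are met.
5. **What is recorded (10, 10.1, 10.4, 13.3.1).** The event is an AE, documented with "severity, outcome and any relationship to investigational product" among its details. The e-CRF is hosted at the KKS, so the entry does reach the KKS database. Section 10.1 sets no deadline for it and no review that it would trigger.
6. **Expectedness assessment (10.2).** Notice within 1 working day, and the Principal Investigator's review of seriousness, relatedness and expectedness, are written for SAEs. The exempted case starts neither.
7. **SUSAR reporting (10.3).** The limit of 15 calendar days for a non-fatal, non-life-threatening SUSAR runs from first notification. No notification step is written for the exempted case.
8. **Committee (13.1).** The safety meeting reviews SAEs and SUSARs. The exempted case is in neither list.

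For GvHD after a DLI on study drug, steps 1, 2, 5, 6 and 8 apply whatever the causality grade. Steps 3, 4 and 7 apply only if the event is also suspected to be related. Because 6.7.2 stops study drug at relapse, a DLI on study drug means one given before relapse.

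| | SAE as reported under 10.2 | GvHD admission exempted by 9.2.2(c) |
|---|---|---|
| Notice to the KKS | 1 working day | AE entry, no stated deadline |
| Expectedness assessment | Principal Investigator | none triggered |
| Committee case review | yes | none stated |

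**The case against.** The strongest reply is that the protocol keeps several safeguards, and most of it stands. Fatal, life-threatening or disabling GvHD is still an SAE. The exempted event is still an AE with a causality grade in a database that the KKS hosts, and section 4 requires GvHD to be documented on a dedicated chart. Related events fall under the dose rules of 6.2.1, and treatment can be ended under 5.8. Section 11.3 compares AE numbers by arm, which for a complication as hard to attribute as GvHD may tell more than single cases. Sections 9.4, 9.5 and 10.3 are not amended, so the SUSAR duty itself remains. None of this supplies the missing link, however: a duty to report on notification does not work where no notification is written.

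Four stronger readings are tempting, and the protocol does not support them.

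- A reader might infer that every hospitalised GvHD case drops out of the safety system. It does not, for the reasons just given.
- A reader might set the yearly committee looks against the 15-day SUSAR limit as a measure of delay. A properly reported SAE that is not a SUSAR also waits for the scheduled look, so that interval is not caused by the exception.
- A reader might take GvHD to be the only acknowledged unknown. Sections 3.4, 6.1.2.2 and 6.2.2 name others: toxicity alongside post-transplant prophylactic medication, CYP3A4 inducers and haematological toxicity.
- A reader might conclude that the committee sees nothing on GvHD. Section 13.1 gives it a safety analysis at 20 patients and yearly, and AE counts by arm can include GvHD.

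The DLI part may concern few patients or none, since DLI is generally not planned. The relatedness part does not depend on DLI.

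**Conclusion.** The point holds for GvHD that is serious by hospitalisation alone and is either suspected to be related to study drug or follows a DLI given on study drug. Followed as written, the protocol provides no timed notification, no triggered expectedness assessment and no committee case review for these admissions. For the suspected and unexpected ones, this conflicts with its own duty in 10.3.

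The size cannot be given as a patient count, because the protocol states no rate of GvHD, GvHD admission or DLI. The measurable contrast is 1 working day against no stated deadline. The SUSAR part also assumes that at least some related GvHD would be unexpected against the product information, which is not reproduced in the protocol. The matter is still open to correction: section 11.3 reports 45 of 200 planned patients randomised after 40 months, so further patients may be treated under this rule.

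This is a worthwhile and inexpensive safety correction. It does not show that harm has been missed.

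**What to change.** Keep item (c) of 9.2.2 as "Hospitalization due to GvHD or coherent treatment" and add after it: unless the GvHD is suspected (certain, probable or possible by 10.4) to be related to study drug or follows a DLI given on study drug. State that the excepted cases are reported under 10.2. Naming the three grades also covers the grade of certain, which 9.3 does not mention.

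The cost is one clause and an unknown number of extra SAE forms. It may be more than a few: in 10.4, possible includes events that disease or other drugs could equally explain, which will fit a good deal of GvHD arising on treatment. Because investigators are blinded, the forms will come from both arms. GvHD judged unlikely or not related, and not following a DLI on study drug, stays exempt, so the exception keeps its main purpose.
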